Two groups will be evaluated in this PhD study – healthy volunteers and PAD patients (figure 1). This will be a single-blinded placebo controlled cohort study. All healthy volunteers will receive active -40mmHg

Mechanistic Insights into changes in peripheral blood flow following intermittent negative pressure.

INP while PAD patients will receive either an active device (-40mmHg INP) or placebo device (-10mmHg INP).

Randomisation

This will be a single-blinded study. The patients will not know whether they have been assigned to the active or placebo device. The researcher will know which device a patient has been assigned to. 80 PAD patients will be recruited in total. The first 20 PAD patients will not be randomised and will be assigned the active device. The subsequent 60 PAD patients will be randomised on a 2:1 basis with 40 patients assigned the active device and 20 assigned placebo. This will allow for more mechanistic studies to be carried out on patients receiving active -40mmHg INP. Patients will be randomised to either active or placebo using an online randomisation programme.

Patients will be told which device they were assigned to at the end of the study.

At the start of the study, eligible patients with an ABPI <0.9 will be approached in wards and clinics by the study team and vascular surgery team. Patients will be given an invitation letter along with an information sheet and reply slip. The study team will offer the patients INP and the patients will be trained to use the Flow-Ox themselves.

Group 1. 40 healthy subjects will be approached by e-mail and posters at Ninewells. Healthy volunteers will be studied to explore the effects of acute application (1 session) and repeated application (daily for up to 5 days) of INP on measurements described above. Importantly for the purposes of this PhD project, this group of subjects will allow us to explore the mechanistic effects of INP on normal physiology.

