Group 2. 80 patients with PAD will be recruited from in-ward patients and from outpatient vascular clinics. Patients will be recruited by the Vascular Surgery team lead by the Consultant Vascular Surgeon who is the second Academic Supervisor of the PhD student. Patients will be randomised to active INP device (-40mmHg) or placebo INP device (-10mmHg). 20 patients in total will receive the placebo device and 60 will receive the active device. The effects of INP on the measurements described above will be made at baseline (before application of INP), following 1 session of INP (acute effects) and following 4-8 weeks of daily INP. As this is a PhD project, not all patients will undergo 8 weeks' of INP. Based on the initial studies of the shorter 4-week duration, we will be able to examine how many patients will be tested for 8 weeks.

Mechanistic Insights into changes in peripheral blood flow following intermittent negative pressure.

Before application of INP, anthropometric baseline measurements (height, weight) will be taken from all participants at Level 7, Division of Systems Medicine, Ninewells Hospital. For patients, medical notes will be reviewed for clinical characteristic including information on past medical history, drug therapy and blood biochemistry.

[figure not shown]

Figure 1:Flow Chart of study design and measurement techniques.

FLOW-Ox System:

Application of INP will be made using the Flow-Ox machine, a CE marked device provided by Otivio as a gift (Otvio AS, Oslo, Norway) (Figure 1). Participants will be asked to be comfortably clothed and seated (with a 130-degree angle between their hip and knee joint) for 20 minutes prior to the start of the experiment. They will be asked to place a leg into the Flow-Ox chamber which is a molded polyethylene

Mechanistic Insights into changes in peripheral blood flow following intermittent negative pressure.

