pressure chamber that is designed specifically in a boot shape to fit the leg. The other leg will form the control and will be placed outside the pressure chamber in a normal atmospheric pressure. The internal padding of the boot will allow insertion of the leg without pressure points on the skin. The boot will be sealed below the knee with a thermoplastic elastomer. This will help to apply the negative pressure to the lower limb. The pressure will be continuously monitored by a pressure transducer attached within the boot. Firstly, a two-five-minute baseline recording without any pressure change (atmospheric pressure, 760mmHg) will be recorded. Consecutively INP will be applied for one hour, twice per day, using a cyclical protocol that comprises of 10 seconds of -40mmHg negative pressure and 7 seconds of atmospheric pressure (as outlined by Sundby et al 2016) (5). The placebo device delivers negative pressure of -10mmHg by the same cyclical protocol as the active device but does not alter blood flow. For studying the longer-term effects of INP application, participants will be trained to use the Flow-Ox machine in their homes and will return to the hospital for follow-up assessments at 4 or 8 weeks. Patients will be contacted weekly (and where appropriate visited at their homes) to ensure no problems are encountered and to encourage adherence to the study.

Figure 2: Illustration of patient set up with the Flow-ox boot.

Mechanistic Insights into changes in peripheral blood flow following intermittent negative pressure.

Blood Samples

40ml of blood will be obtained from each study subject for serum markers of inflammatory and oxidative stress. Serum will be analysed using Bio-Plex® Precision Prokits™ (BIO-RAD laboratories) for IL-1 β , IL-6, IL-10, TNF- α , CRP, E-selectin, sICAM-1. Peripheral blood mononuclear cells (PBMC) will be extracted for analysis of expression of Nrf2 by qRT-PCR analysis, measuring the expression of Nrf2-target genes. The genes to be analysed will include those encoding GCLC, GCLM, GSR1 and SLC7A11 (synthesis and regeneration of GSH), TXNRD1 and SRXN1 (reduction of protein thiols), GPX2, HMOX1, PRXD1 and PRDX6 (ROS scavenging and stress biomarkers), AKR1B10, AKR1C1, AKR1C2 and NQO1 (detoxification of oxidation products). Western blotting will be performed to measure the protein levels of all Nrf2-target genes that are expressed in PBMCs as a means of corroborating qRT-PCR results.

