The extent of oxidative stress will be estimated by measuring reactive oxygen species (ROS) using 2',7'-dichlorodihydrofluorescein, malondialdehyde by an LC-MS assay, and reduced glutathione (GSH) and oxidised glutathione (GSSG) by a standard LC-MS assay.

The surplus blood samples will be stored for 15 years at -80°C in the department, Division of Systems Medicine at Ninewells Hospital, and will be registered with Tayside Biorepository.

Laser Doppler Imaging

Laser Doppler imaging (using the Moor Instrument FLPI system) will be used to measure microvascular endothelial functions and blood perfusion of the lower limbs and arm. This test will be a good measure of how the lower limb circulation changes after INP application and if any systemic changes in microcirculation occur in the arm. The laser will be mounted on an adjustable arm attached to a portable stand. This will be positioned 20-30 cm above the skin to capture the image. The camera records blood flow in the superficial microvessels (arterioles, venules and capillaries) up to 1mm deep in skin. Repeated scans will be obtained and the perfusion calculated in arbitrary units. The microvessels of the lower limb will be stimulated using iontophoresis of acetylcholine (ACh) and sodium nitroprusside (SNP) to assess endothelium-dependent and –independent mechanisms, respectively.

At each assessment, wounds will be photographed using the laser Doppler imager and measured using appropriate software (eg. Photoshop).

Mechanistic Insights into changes in peripheral blood flow following intermittent negative pressure.

Flow-Mediated Dilatation

This test assesses endothelial function of the macrocirculation of the (brachial artery) through flow mediated changes. This test involves using a high resolution ultrasound probe (5-8 MHz) to measure changes in the diameter of brachial artery following 5-minutes of ischaemia applied to the forearm using a blood pressure cuff inflated above systolic blood pressure (normally 200mmHg). The measurement of brachial artery diameter will be taken on three occasions; baseline, during occlusion and after deflation. This test is not anticipated to have any risk to the participants.

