For adults who lose capacity their previous wishes will remain legally binding and this will remain valid unless the protocol changes significantly. If this occurs and further consent is required from a participant who has lost capacity, the appropriate person will be asked for their consent. In all cases the CI or delegate will consult with carers and take note of any signs of objection or distress from the participant – the participant will be withdrawn if they raise objection. Where appropriate the participant will be withdrawn from any further clinical intervention and agreement will be sought from a carer to allow data collection.

The informed consent process will be conducted in compliance with TASC SOP07: Obtaining Informed Consent from Potential Participants in Clinical Research

Mechanistic Insights into changes in peripheral blood flow following intermittent negative pressure.

Ineligible and Non-recruited Participants

The reason(s) for ineligibility will be explained to participants and any questions they have will be answered. They will be thanked for their participation in screening.

Withdrawal Procedures

Participants are free to withdraw from the study at any time. If at any time the participant formally withdraws his/her consent for future participation and disclosure of future information, no further evaluations will be performed and no additional data should be collected. Data collected before withdrawal will be retained and used in the study analysis, unless the participant requests otherwise. If participants withdraw during the visit, they will have the option to request that data already collected is not to be used in the study.

STUDY & SAFETY ASSESSMENTS

Patients will undergo their standard care as routine.

PAD patients

Research bloods (40 mls) will be obtained at the research site following informed patient consent and other study procedures such as pain chart, laser imaging, arterial stiffness and ABPI. This usually will occur on the 1st day in the designated research department, Division of Systems Medicine at Ninewells Hospital, and on two follow-up visits, after one INP session and 4 to 8 weeks after daily INP use. We do not envisage that any of these will interfere with their care or are likely to cause any harm. Nevertheless, any adverse events that may potentially be related to the study will be reported to the CI and clinical Vascular Team who will administer appropriate clinical action.

Healthy Volunteers

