Data entry and checking will be undertaken by a single entry with a second look. The data entry and checking process will be decided according to risk. Data that is recorded in the CRF that is not source document in itself will be consistent with the source documents or the discrepancies explained. Checks will be made on all missing values and values out with normal or expected ranges and that values entered

Mechanistic Insights into changes in peripheral blood flow following intermittent negative pressure.

are of the correct type: i.e. numerical instead of text. Logical checks will be performed to ensure consistent reporting between relevant fields and that there are no differences between fields. Data checking will continue until all missing data and/or inconsistent values have been corrected or clarified. When data checking is complete, with no outstanding data queries, the database will be locked, using the Protect Worksheet function of EXCEL, as FINAL RESULTS. The EXCEL spreadsheet will remain archived on the Dundee University secure server for 5 years for the retention of essential documents, thereafter it will be deleted.

STATISTICS AND DATA ANALYSIS

Sample Size Calculation

As this is a PhD project exploring mechanisms of vascular changes, precise power calculations have not been obtained. The results from this PhD project will guide us regarding subsequent power calculations. However, based on our previous work exploring mechanisms of changes in vascular function using various interventions, n=25 subjects will provide at least 80% power and 5% significance to detect a 20% before and after difference within subjects in the vascular function markers proposed in this study.

Proposed Analyses

Changes in blood flow and endothelial function in the lower limbs using laser Doppler perfusion imaging and iontophoresis will be compared primarily within each group and also between patient groups at baseline, after 1 INP session and after the last INP (4 to 8 weeks) is applied. The primary outcome measure will be the change in peak blood flow response to acetylcholine and sodium nitroprusside.

Data will be analysed using widely available statistical analysis software such as SPSS. Analytical methods will include t-tests, chi-square, ANOVA, correlation and regression as appropriate.

Mechanistic Insights into changes in peripheral blood flow following intermittent negative pressure.

STUDY MANAGEMENT AND OVERSIGHT ARRANGEMENTS

Study Management

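### The only power figure is for within-subject change; the randomised 40 versus 20 comparison has none and is not named as the basis for attributing an effect to the active device

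*Combined protocol and SAP*

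**What the plan says.** The Sample Size Calculation states that "precise power calculations have not been obtained", because this is an exploratory PhD project whose results will inform later calculations. It then offers one figure, attributed to earlier work: "n=25 subjects will provide at least 80% power and 5% significance to detect a 20% before and after difference within subjects". No SD, sidedness or dropout allowance is given.

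Under Randomisation, the first 20 PAD patients all receive the active device without randomisation. Then: "The subsequent 60 PAD patients will be randomised on a 2:1 basis with 40 patients assigned the active device and 20 assigned placebo". The reason given for the imbalance is "This will allow for more mechanistic studies to be carried out on patients receiving active -40mmHg INP". The Group 2 paragraph confirms the totals: "20 patients in total will receive the placebo device and 60 will receive the active device".

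Proposed Analyses makes comparison within each group the main one and comparison between patient groups an addition, using t-tests, ANOVA or regression as appropriate. I read the between-group part as including active versus placebo.

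The FLOW-Ox System section says of the control: "The placebo device delivers negative pressure of -10mmHg by the same cyclical protocol as the active device but does not alter blood flow". It also says that the leg left outside the chamber serves as a control.

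**The concern.** The study is described as placebo controlled, yet its main analysis asks whether each group changed from its own baseline, and its only power statement answers that same question. A before-after change in the active arm mixes any device effect with placebo response and the effect of repeat testing. The randomised difference between arms removes what the two arms share. The plan includes that comparison but gives it no power, detectable difference or expected precision, and does not say that it settles whether the active device does more than placebo.

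Two misreadings are possible. A non-significant 40 versus 20 result could be taken as no device effect when the comparison was too imprecise to tell. And if both arms changed alike, a significant active arm beside a non-significant, smaller placebo arm could be taken as a device effect.

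**Working it through.** **Inputs from the documents:** n=25, power at least 80%, 5% significance, 20% within-subject difference (Sample Size Calculation); 40 and 20 randomised, plus 20 unrandomised active patients (Randomisation).

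**Assumptions:** two-sided test; 20% read as 20 percentage points, with the SD of change in the same units; equal SDs in the arms; full completion. The SD is back-solved because none is stated.

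**1. The plan's own figure.** Without an SD, n=25 cannot be reproduced. For a paired t-test, power comes from the noncentral t with n−1 df and noncentrality (20/SD)×√n.
- n=25 at exactly 80%: 20/SD = 0.584, noncentrality 0.584×5 = 2.92, SD = 20/0.584 = 34.2.
- n=25 at 90%: 20/SD = 0.676, SD = 20/0.676 = 29.6.

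Because the plan says at least 80%, 34.2 is the largest SD compatible with the sentence under a two-sided test.

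**2. Randomised contrast, unadjusted t-test on change.** Noncentrality = (20/SD)×√(40×20/60) = (20/SD)×3.651, with 58 df and critical value 2.002. The 95% CI half-width is 2.002×SD×√(1/40+1/20).

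| SD | Noncentrality | Power at 20 points | Difference detectable at 80% | 95% CI half-width |
|---|---|---|---|---|
| 34.2 | 2.13 | 55% | 26.7 | 18.8 |
| 29.6 | 2.47 | 68% | 23.1 | 16.2 |

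Power reaches 80% only if the SD is about 25.6 or less. At that SD, n=25 would have about 96% power within subjects.

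**3. Same contrast, adjusted for baseline.** With equal baseline and follow-up variances and correlation ρ, the SD of change is multiplied by √((1+ρ)/2), and one df is lost (57). The values of ρ are assumed.

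| ρ | Factor | Power, SD 34.2 | Power, SD 29.6 |
|---|---|---|---|
| 0.3 | 0.806 | 74% | 85% |
| 0.5 | 0.866 | 68% | 80% |
| 0.7 | 0.922 | 62% | 75% |

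**4. Adding the 20 unrandomised active patients.** At SD 34.2, noncentrality = 0.584×√(60×20/80) = 2.26, which gives 61% against 55%.

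**5. Withdrawals.** The plan says "Participants are free to withdraw from the study at any time". With an assumed 10% loss (36 versus 18), unadjusted power at SD 34.2 falls to 51%.

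**6. Reading two within-group tests side by side.** Suppose both arms truly change equally, which departs from the plan's statement about placebo. The chance that active is significant and placebo is not is the product of two probabilities.

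| SD | True change in both arms | 40 active | 60 active |
|---|---|---|---|
| 34.2 | 20 | 0.950×0.302 = 29% | 0.994×0.302 = 30% |
| 34.2 | 10 | 0.437×0.763 = 33% | 0.604×0.763 = 46% |
| 29.6 | 20 | 0.986×0.182 = 18% | 0.999×0.182 = 18% |
| 29.6 | 10 | 0.550×0.700 = 38% | 0.731×0.700 = 51% |

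In every row the between-arm test is significant in 5% of trials.

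**The case against.** - **The plan disclaims a formal calculation.** It does, and the n=25 sentence is expressly limited to change within subjects. A reader might infer a miscalculation or an unfounded claim of power for active versus placebo. The documents support neither: nothing in the sentence is shown to be wrong, and it claims nothing for 40 versus 20. The gap is one of justification.
- **There is another control.** The untreated leg is measured concurrently and partly controls for repeat testing, so the between-arm difference is not the sole safeguard. But that leg is not a blinded placebo, Proposed Analyses sets no leg-to-leg test, and a secondary objective asks whether treatment of one limb acts systemically. If it does, the untreated leg is affected too.
- **The 55% is the least favourable case.** This is correct. It takes the largest compatible SD and an unadjusted test, although the plan allows regression. It should be quoted only with its range.
- **Placebo has fewer than 25 patients.** A reader might infer that the plan fails its own requirement. Power for a 20-point change with n=20 is 70% at SD 34.2 and 82% at SD 29.6, but the placebo device is said not to alter blood flow, so that power is hardly needed. The point is minor.
- **The 2:1 split.** It is deliberate and explained, and is not at issue.
- **The plan never says it will contrast significant with non-significant arms.** That is true, and it does plan a between-group comparison. The 18-51% shows what one added sentence would prevent; it is not an error already made.

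**Conclusion.** The concern holds as a gap in analysis and sample-size justification. The single power figure does not reach the only randomised comparison, and the plan does not name that comparison as the basis for attributing a change to the active device rather than to placebo effects. A reader might conclude that the trial is underpowered for active versus placebo. The documents do not establish that, because the SD of change is missing. Over the cases worked, power for a 20-point difference runs from about 55% (SD 34, unadjusted) to about 85% (SD 30, adjusted, correlation 0.3), and a smaller SD would raise it further. Withdrawals would lower it. All of this rests on the back-solved SD, a two-sided 5% test, equal SDs and, for the adjusted figures, assumed correlations.

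**What to change.** No extra patients are needed.

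1. In Proposed Analyses, add: *Any effect of the active over the placebo device will be judged from the randomised between-arm difference in change (40 versus 20), adjusted for the baseline value, with its 95% CI, and not from a significant change in one arm and a non-significant change in the other.* Within-group and healthy-volunteer analyses stay as planned for the mechanistic questions.
2. After the n=25 sentence, state that it applies to within-subject change only and not to active versus placebo. Then give the expected precision for 40 versus 20, using the SD of change from the sponsor's earlier work, or call that comparison exploratory.

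The cost is a less favourable power statement and a commitment on how a device effect is judged. The first 20 unrandomised active patients are left out of that one comparison (55% instead of 61% power, unadjusted, at SD 34) and remain in the within-group analyses. Under the correlations assumed above, baseline adjustment recovers more power than leaving them out loses.

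### For PAD patients, the plan leads with before/after change within groups; the randomised active-versus-placebo comparison ranks second, has no assigned method, and is not limited to the randomised patients

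*Combined protocol and SAP*

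**What the plan says.** Proposed Analyses states that changes in lower-limb blood flow and endothelial function will be "compared primarily within each group and also between patient groups at baseline, after 1 INP session and after the last INP". It then says: "The primary outcome measure will be the change in peak blood flow response to acetylcholine and sodium nitroprusside". The methods are one general list (t-tests, chi-square, ANOVA, correlation, regression), tied to no particular comparison.

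Sample Size Calculation concedes that "precise power calculations have not been obtained". Its only power statement is for before/after change: "n=25 subjects will provide at least 80% power and 5% significance to detect a 20% before and after difference within subjects". No SD is given.

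Under Randomisation: "The first 20 PAD patients will not be randomised and will be assigned the active device". Then: "The subsequent 60 PAD patients will be randomised on a 2:1 basis with 40 patients assigned the active device and 20 assigned placebo". The stated reason is mechanistic: "This will allow for more mechanistic studies to be carried out on patients receiving active -40mmHg INP". The description of Group 2 counts 60 active and 20 placebo patients without setting the first 20 apart, and no analysis population is defined anywhere.

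The FLOW-Ox System section describes the placebo device as leaving blood flow unchanged. It also names a second control: "The other leg will form the control and will be placed outside the pressure chamber". Proposed Analyses makes no use of that leg.

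**The concern.** PAD patients continue their standard care, are contacted weekly, and are measured repeatedly. A change in the active arm between baseline and 4 to 8 weeks mixes these influences with any effect of INP. The randomised placebo arm is there to separate them, yet the plan puts the comparison that uses it second.

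Three gaps follow:

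- **Rank.** The lead PAD result, read as the plan orders it, cannot tell an INP effect from a shift common to both arms.
- **Method.** Nothing says how active and placebo will be compared, and the 25-subject statement does not bear on 40 versus 20.
- **Analysis set.** One third of the active patients (20 of 60) were not randomised and were enrolled first. Nothing keeps them out of the comparison with placebo.

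Setting the placebo arm's own before/after test beside the active arm's does not solve the first problem. With 20 patients against 40 or 60, the active arm can reach significance and the placebo arm miss it through size alone.

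**Working it through.** **Inputs from the documents.** 25 subjects, at least 80% power, 5% significance, 20% within-subject change (Sample Size Calculation); 20 non-randomised active patients, then 40 active and 20 placebo (Randomisation).

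**Assumptions.** 20% is read as 20 points on an additive scale; tests are two-sided; SDs are equal in both arms. The shifts, SDs and correlations are hypothetical.

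**1. The plan's own figure.** It cannot be reproduced without an SD, so it is solved backwards. For a paired t-test with n = 25 and 80% power, the noncentral t gives a standardised change of 0.584. The largest compatible SD of change is 20 / 0.584 = 34.2 points. If the 5% were one-sided it would be 39.1, so 40 serves as the upper value and 25 as a lower one.

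**2. A shift common to both arms, no device effect, SD 34.2.** Each within-arm test has noncentrality shift × √n / SD. The pattern probability is P(active significant) × [1 − P(placebo significant)].

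| Common shift (points) | Placebo significant, n=20 | Active significant, n=40 | Active significant, n=60 | Active yes, placebo no (40 v 20) | Active yes, placebo no (60 v 20) |
|---|---|---|---|---|---|
| 2.5 | 6% | 7% | 9% | 7% | 8% |
| 5 | 10% | 15% | 20% | 13% | 18% |
| 10 | 24% | 44% | 60% | 33% | 46% |
| 15 | 46% | 77% | 92% | 42% | 49% |

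Example at 10 points: 0.437 × (1 − 0.237) = 0.334. With 40 active patients and a 10-point shift, the pattern is 42% at SD 25 and 28% at SD 40. The within-arm rejections correctly detect a change; the error would lie in attributing it to INP.

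**3. The randomised contrast under the same shifts.** Simulated ANCOVA at 40:20 (20,000 trials, baseline–follow-up correlation 0.5) rejects 5.3%, 5.1%, 5.1% and 4.9% of the time, which is the nominal level.

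**4. Pooling the first 20.** They are 20/60 of the active patients, so if their mean change differs by b points for reasons other than the device, the 60:20 estimate moves by b/3. For b = 10, 20 and 30 that is 3.3, 6.7 and 10 points. Simulated ANCOVA at 60:20 then rejects about 7%, 11% and 20% of the time with no device effect.

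**5. What the randomised contrast can deliver.** ANCOVA residual SD = SD of change / √(2(1−r)) × √(1−r²), where r is the baseline–follow-up correlation. At SD 34.2 and r = 0.5: 34.2 / 1 × 0.866 = 29.7. The standard error is 29.7 × √(1/40 + 1/20) = 8.1, and the 95% half-width is 2.00 × 8.1 = 16.3 points.

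| SD of change | Power for 20 points, change score | Power, ANCOVA (r = 0.8 to 0.3) | ANCOVA 95% half-width (points) |
|---|---|---|---|
| 25 | 82% | 86–95% | 11–13 |
| 34.2 | 55% | 60–74% | 15–18 |
| 40 | 44% | 47–60% | 18–21 |

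The within-active change at n = 40 has a half-width of 11 points at SD 34.2. If only 32:16 reach the late visit, ANCOVA power at SD 34.2 is 50–64%.

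**The case against.** This is an openly exploratory mechanistic PhD project with no efficacy claim or decision rule, and within-subject change fits its aims. The between-group comparison is planned at all three time points, and the listed methods include suitable ones. The plan nowhere proposes comparing two within-arm p-values or pooling the first 20. The control leg could remove influences acting equally on both legs. An SD of 34.2 is an upper limit: at SD 15 and a 15-point shift, the pattern of active significant and placebo not falls to about 1%.

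Part of this stands. The figures are conditional illustrations, pooling is merely not excluded, and standard care and weekly contact cannot explain a change after a single session. Study groups are elsewhere defined as healthy volunteers and PAD patients, so reading the between-patient-group comparison as active versus placebo is an interpretation, though the natural one. On the other reading, the placebo contrast is specified even less.

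The rest does not remove the problem. Exploratory status excuses an imprecise power statement; it does not make a before/after change attributable to INP when a randomised control is available. A small SD lowers the discordant pattern only because both arms then detect the common shift; the within-active result is still not attributable to INP. The control leg cannot replace placebo, because a secondary objective asks whether INP acts systemically, and a systemic effect would pull the leg difference towards zero.

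**Conclusion.** The concern holds and should be fixed. It rests on the text: within-group change comes first, the randomised contrast has no assigned method, and no analysis set separates the 20 non-randomised active patients. It applies to PAD patients only, and the attribution problem is clearest at 4 to 8 weeks.

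The size depends on an SD and a common shift that the documents do not give. Under the hypothetical 10-point shift at SD 34.2, the lead analysis would show a significant active-arm change in 44% of trials with no device effect, against about 5% for the randomised ANCOVA. Any bias from pooling would be one third of whatever difference exists between the first 20 patients and those randomised later.

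**What to change.** In Proposed Analyses, state that for PAD patients the lead analysis, and any conclusion that INP changes vascular function, rests on active versus placebo in the 60 randomised patients (40 v 20). Specify ANCOVA of peak response with baseline peak response as covariate, separately for acetylcholine and sodium nitroprusside, at each planned follow-up, reported as estimates with 95% confidence intervals. Say how 4-week and 8-week assessments are handled in the late estimate. Report within-group changes, the first 20 patients, the healthy volunteers and any control-leg comparison (where both legs are measured) as supportive and descriptive.

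In Sample Size Calculation, state that the 25-subject figure does not apply to this contrast, and give its expected precision.

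The cost is a few sentences, plus the approvals the protocol requires for any amendment. Visits, measurements and recruitment stay as planned. The drawback is lower power and wider intervals than for the before/after analysis, as shown in the second table; presenting estimates with intervals suits an exploratory study.

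### The plan does not specify adjustment for each patient's own baseline in the randomised active-placebo comparison (40 v 20), and leaves open what the primary 'change' is measured from

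*Combined protocol and SAP*

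**What the plan says.** The analysis plan is the short Proposed Analyses text under Statistics and Data Analysis.

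- **What is compared.** The subject of the main sentence is "Changes in blood flow and endothelial function in the lower limbs using laser Doppler perfusion imaging and iontophoresis". These are to be compared first within each group, and "also between patient groups at baseline, after 1 INP session and after the last INP".
- **Primary outcome.** "The primary outcome measure will be the change in peak blood flow response to acetylcholine and sodium nitroprusside". The reference point of the change is not given.
- **Methods.** "Analytical methods will include t-tests, chi-square, ANOVA, correlation and regression as appropriate". No model, covariate or adjusted estimate is named.
- **Data available.** Study Design, Group 2, has the measurements "made at baseline (before application of INP), following 1 session of INP (acute effects) and following 4-8 weeks of daily INP", so every patient should have a baseline value of each response.
- **Allocation.** Under Randomisation, the first 20 PAD patients all receive the active device without randomisation. "The subsequent 60 PAD patients will be randomised on a 2:1 basis with 40 patients assigned the active device and 20 assigned placebo".

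**The concern.** The contrast among the 60 randomised patients is the only part of the study that separates an INP effect from time, repeat testing and placebo response. It is small, with 20 patients on placebo, and the sample-size text covers only within-subject change. Precision that can be had without extra patients is therefore worth taking.

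The wording leaves two analyses open. A change from the pre-INP visit cannot be compared between groups at baseline, because it does not yet exist there. Listing baseline as a comparison point therefore leaves room for a visit-by-visit reading, in which the change is the rise in flow during iontophoresis and the arms are compared on that rise at each visit. On that reading the later comparisons use post-INP values alone. On the other reading they use change scores. In neither case does the plan call for a model with baseline as a covariate.

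A test of active against placebo at baseline adds nothing among randomised patients, where any difference is due to chance. The choice among the three analyses also stays open until the data are in, and the Randomisation section says that the researcher knows each patient's device.

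**Working it through.** **1. The plan's own figure.** The Sample Size Calculation section states n = 25 for at least 80% power at 5% significance to detect a 20% before-after difference within subjects. It gives no SD, so the figure cannot be reproduced. It can only be inverted. For a two-sided paired t-test it implies an SD of the within-subject difference of 34.2%. The normal formula gives 20 × √25 / (1.960 + 0.842) = 35.7%. No figure is given for active against placebo.

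**2. Inputs for 40 v 20.** The arm sizes come from the Randomisation section. My assumptions are a two-sided 5% test, no dropout, equal SDs at both visits, and a baseline-to-follow-up correlation r of 0.3 to 0.8. The documents give no r.

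**3. Formulas.** Let SD be the between-patient SD of the response at one visit. The SE of a difference between arms is √[V × (1/40 + 1/20)] in SD units, where V is:

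- post-INP value only: V = 1
- change from baseline: V = 2(1-r)
- baseline-adjusted: V = 1-r²

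For r between 0 and 1, 1-r² is below 1. It is also below 2(1-r), because their ratio is (1+r)/2. At r = 0.6 the three values are 1, 0.80 and 0.64.

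**4. Power for an assumed true difference of 0.6 SD** (non-central t, 58 degrees of freedom; 57 when adjusted):

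| r | Post only | Change score | Adjusted |
|---|---|---|---|
| 0.3 | 58% | 44% | 62% |
| 0.5 | 58% | 58% | 70% |
| 0.6 | 58% | 67% | 77% |
| 0.7 | 58% | 79% | 85% |
| 0.8 | 58% | 93% | 95% |

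At r = 0.6, the differences detectable with 80% power are 0.78, 0.70 and 0.62 SD. Estimating the baseline slope inflates the adjusted variance by about 1/56, or 1.8%. That lowers the 77% to 76%.

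**5. The same check on the plan's scale.** Assume an SD of the difference of 34.2% (step 1) and a true active-placebo difference of 20 points. The single-visit SD is then 34.2 / √[2(1-r)].

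| r | Post only | Change score | Adjusted |
|---|---|---|---|
| 0.3 | 70% | 55% | 74% |
| 0.5 | 55% | 55% | 68% |
| 0.6 | 47% | 55% | 65% |
| 0.7 | 37% | 55% | 62% |
| 0.8 | 26% | 55% | 60% |

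The ordering is the same: adjustment is best in every row.

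**6. Chance imbalance.** The SE of the baseline difference between arms is √(1/40 + 1/20) = 0.274 SD, with a 95% range of about ±0.54 SD. The chance of an imbalance above 0.3 SD in either direction is 27%. Given an observed baseline difference D, a post-only estimate is shifted by r × D and a change-score estimate by -(1-r) × D. With D = 0.3 SD and r = 0.6, the shifts are 0.6 × 0.3 = +0.18 SD and -0.4 × 0.3 = -0.12 SD. Adjustment removes the linear part.

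**The case against.** A reader might infer that the plan never uses a patient's own baseline value. The documents do not support that. The sentence is about changes, the primary outcome is a change, and the within-group comparison, which ranks first, is a before-after one. If change means change from the pre-INP visit, the arm comparison already uses baseline. Regression is on the method list, so the plan permits the adjusted model. What stands is that it neither specifies that model nor says what the change is measured from.

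The gain also depends on the reading. The step from 58% to 77% applies only if post-INP values are compared alone. On the more natural change-score reading it is 67% to 77%. It shrinks at high r against change scores (93% to 95% at r = 0.8) and at low r against post-only values (58% to 62% at r = 0.3).

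A reader might also infer that imbalance is likely, or that it biases the result. A 27% chance of more than 0.3 SD does not make it likely, and under randomisation it causes no bias on average.

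Finally, the term patient groups is not tied to the randomised 40 v 20. Study Design names healthy volunteers and PAD patients as the two groups, and the Group 2 totals are 60 active and 20 placebo, including the 20 non-randomised patients. In those comparisons a baseline difference need not be chance. That is fair, and it is why the fix has to state the analysis set. That the study is an exploratory PhD project limits how much rests on this contrast, but not the case for a change that costs nothing.

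**Conclusion.** The point holds as a gap in specification with a free remedy, not as a wrong analysis already chosen. Baseline adjustment of the randomised contrast is not prespecified, and the reference point of the primary change is undefined. Across the assumed r of 0.3 to 0.8 and a 0.6 SD effect, adjustment adds 4 to 37 percentage points of power over post-only values and 2 to 18 over change scores. At r = 0.6 the gains are 19 and 10 points. The size rests on the assumed r, effect, equal SDs and no dropout. The ordering of the three analyses does not depend on the effect size, and it holds for any r that is not close to 0 or 1. Chance imbalance affects the estimate given the observed baselines, not its average validity.

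**What to change.** In Proposed Analyses:

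1. Define the change: state whether it is measured from the pre-INP visit or is the rise during iontophoresis at one visit.
2. For the active-placebo contrast, use the 60 randomised patients and exclude the first 20 non-randomised active patients.
3. Regress the post-INP peak response on device and the patient's own baseline value of that response. Do this separately for acetylcholine and sodium nitroprusside, and separately at the one-session visit and the late visit. Report the adjusted active-minus-placebo difference with a 95% CI.
4. Apply the same model to FMD%, pulse wave velocity, ABPI and pain.
5. Replace any active-placebo test at baseline with a descriptive table for the randomised patients.

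The cost is a few lines of text. The model is a standard procedure in SPSS, which the plan already names, and it needs no new data or patients.
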